6.4 Detailed rules for determination of analysis population set and flow chart

- (1) No investigational device is implanted: Subjects obtain random numbers but do not use any study-related treatment (implantation study group, control group or third party products);
- (2) Violation of inclusion and exclusion criteria: The subjects do not meet the inclusion criteria or meet the exclusion criteria set in the study protocol, and the violation of this protocol will seriously affect the results of primary efficacy endpoints; the sponsor, investigators and statisticians will jointly determine through a blind review meeting whether the protocol violation will seriously affect the results of primary efficacy endpoints;
- (3) Loss to follow-up during the trial: Subjects are unable to obtain the fracture union rate 24 weeks after the primary endpoint surgery;
- (4) Cross enrollment: Subjects randomly assigned to the study group receive the control products, while subjects randomly assigned to the control group receive the investigational products;
- (5) Out-of-window time: The difference between the follow-up date at 24 weeks after primary endpoint surgery and the surgery date do not fall within the range of [140, 196], and the violation of this protocol may seriously affect the results of primary efficacy endpoints; the sponsor, investigators and statisticians will jointly determine through a blind review meeting whether the protocol violation will seriously affect the results of primary efficacy endpoints;
- (6) Out-of-specification use of investigational products: The specifications of the device implanted in the subject are not within the specification range specified in the study protocol;
- (7) Use of third party products: The subjects randomly assigned to the study group or the control group use third party products;

(8) FAS = Number of subjects enrolled in the trial - Number of subjects not implanted with any investigational device;

PPS = FAS - Number of subjects who seriously violate the study protocol;

ATS = PPS + Number of cross-enrolled subjects alone; ATS will be displayed if subjects are cross-enrolled in the trial, while ATS will not be displayed if no cross-enrollment occurs.

Number of subjects who seriously violate the study protocol = Violation of inclusion and exclusion criteria + Loss to follow-up during the trial + Cross enrollment + Out-of-window time + Out-of-specification use of investigational products + Use of third party products;

The priority of serious violations from study protocol: Loss to follow-up during the trial, cross enrollment, use of third party products, violation of inclusion and exclusion criteria, out-of-specification use of investigational products, out-ofwindow time; if the subjects meets the above two or more serious violations, the violations will be classified by priority;

Serious violations from study protocol in the statistical table can be listed according to the actual situation of the data. If the number of subjects who exceed the time window in both the study group and the control group is 0, then such information may not be shown in the table. Meanwhile, the list of subjects who are not implanted with any investigational device or have serious violations from study protocol will be provided, including site number, random number, gender, age, type, reason, FAS, PPS and ATS.

[figure not shown]

Figure 1 Flow chart for determination of analysis population data sets

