7.4. Follow-up Period

For each clinic visit there is a required timeline for the visit, as shown in the Time & Events Table. For each of these visits, the data described in Table 8 must be collected.

	Enrollment			Foll	Follow-up		
	FU 1:	FU2:	FU3:	FU4:	FU5:	FU6:	
Event/Visit	Pre-Op	Surgery	1 week	6 weeks	12 weeks	24 weeks	
	-90 to 0		1 to 14				
	days from		days				
	day of		after	±2			
Required Timing	surgery	0	surgery	weeks	±2 weeks	±4 weeks	
The signing of the informed							
consent form	Х						
Inclusion/Exclusion criteria	Х						
Demographic data and medical							
history enquiry	Х						
Concise patient self-rated health							
measurement scale (SF-12v2)	Х				Х	Х	
EQ5D	Х				Х	Х	
Harris Hip Score					Х	Х	
Subject history	Х						
Urine pregnancy test ¹	Х						
Frontal and lateral X-ray of							
fracture sites	Х		Х	х	х	х	
Surgical reduction and							
intramedullary nail fixation		х					
Surgeon's evaluation on product							
operability during operation		х					
Wound healing assessment ²			Х				
Local physical examination	Х		Х	Х	Х	Х	
Concomitant drugs ³	Х	Х	Х	Х	Х	Х	
Adverse event		X4	Х	Х	Х	Х	
Serious adverse event		X4	Х	Х	Х	Х	
Blood chemistry	Х	X ⁵					

1. Urine pregnancy tests: women of childbearing age only.

2. Wound healing condition is assessed until wound healing.

3. Concomitant Drug Table should include only pain killers and anti-osteoporosis drugs.

4. Adverse events and serious adverse events should be recorded starting at the time of patient randomization.

5. Second Laboratory Test analyses performed during post-op recovery phase per site standard of care. The results closer to the time of surgery will be recorded.

Unscheduled Visits

If in between protocol required visits/telephone contacts, the site study team learns of any interventional treatment that a subject has undergone or study-related reportable adverse events, as defined in Section 8.0, the relevant information will be captured on the appropriate CRFs. All diagnostic radiographic films will be reviewed by the independent radiographic reviewer. All relevant source documentation required to assess the event will be maintained in the subject files and all relevant documentation required for event adjudication will be provided as requested by the Sponsor.

Clinical follow-up

The Investigator will be required to document clinical assessment in the medical and research source documents.

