7.5. Blinding Procedures

Many medical records (source documents) documenting the patient's operative procedure, hospital stay and follow-up visits will not be blinded because implant labels identifying the implanted stems will be provided. As is common in device trials, it will not be possible to blind surgeon investigators or study staff because each group will be implanted with a different implant system, each of which is easily distinguished and has its own instrument set. Blinding of the independent radiographic reviewers and study staff also is not feasible because of small differences in design features that may be distinguished postoperatively (e.g., radiographs).

Blinding practices for this study will include the following:

Patients: Patients will be informed of the 1:1 randomization between the two devices, but will remain blinded as to which implant they actually received until after they have completed all study follow-up.

Implanting surgeon: It is not possible to blind the implanting physician due to his/her contact with the product labeling and IFU.

Independent Radiographic Reviewer (IRR): The IRR will not be blinded to the device implanted due to small differences that may be apparent in the radiographic images.

Medical Records: All medical records (source documents) documenting the implant procedure through hospital discharge and all follow-ups will not be blinded because implant labels identifying the implanted stems will be provided.

Monitors: Monitors will not be blinded because the detachable labels provided with the product identify the product and may be used in the study device accountability records and patient research file for the purpose of device accountability and source document validation.

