10.8. Analysis Sets

All subjects who met the inclusion and exclusion criteria will be eligible for enrollment and will be randomized to either the investigational (TFNA) or the control (PFNA-II) group. The following two analysis sets have been defined for this study:

1) Intent-to-Treat (ITT) Population

This analysis set includes all subjects randomized and implanted with a protocol specified implant, TFNA or PFNA-II. It includes the patients who were treated and withdrew prior to

week 24 due to various reasons. If a patient is randomized to one treatment group, but receives the other group for any reasons, the patient is considered to be part of the treatment group as received. This analysis set will be the primary one for the secondary safety analysis.

2) Per Protocol Population

The Per Protocol Population will consist of the subset of the ITT Population who complete 24 weeks of follow-up with no major protocol deviations (including but not limited to: failure to satisfy all inclusion/exclusion criteria, failure to adhere to all protocol-required restrictions and prohibitions, receipt of prohibited concomitant procedures or therapies, and non-compliance to protocol-specific procedures) as determined by a review of subject data.

This PP population will be the analysis set for conducting the primary and secondary effectiveness endpoint analyses.

Separately from these two populations, any subjects who are enrolled into the study but who do not receive one of the study devices will be summarized separately. This summary will include demographics and reasons for not receiving a study device.
The figure below illustrates these populations:

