EuroQoL (Quality of Life)-5 Dimensions (EQ5D): The EQ5D is a patient reported outcome. It provides a simple descriptive profile and single index value for health status. This health-related, quality of life survey consists of five dimensions (mobility, self-care, usual activities, pain/discomfort, anxiety/depression) each of which can take one of five responses. The responses record five levels of severity (no problems/slight problems/moderate problems/severe problems/extreme problems) within a particular EQ-5D dimension.

PROTOCOL DEVIATION

A protocol deviation is defined as an incident where the Investigator or site personnel did not conduct the study according to the investigational plan, protocol or the Investigator agreement.

Major deviation: Any deviation from patient inclusion and exclusion criteria or patient informed consent procedures.

Minor deviation: Deviation from a protocol requirement such as incomplete/inadequate patient testing procedures, follow-ups performed outside specified time windows, etc.

SERIOUS ADVERSE EVENT

A Serious Adverse Event (SAE) is any untoward event that:

a) led to death,

- b) led to serious deterioration in the health of the subject, that either resulted in
- 1) a life-threatening illness or injury, or
- 2) a permanent impairment of a body structure or a body function, or
- 3) in-patient or prolonged hospitalization, or
- 4) medical or surgical intervention to prevent life-threatening illness or injury or permanent impairment to a body structure or a body function,
- c) led to foetal distress, foetal death or a congenital abnormality or birth defect

NOTE Planned hospitalization for a pre-existing condition, or a procedure required by the

CIP, without serious deterioration in health, is not considered a serious adverse event.

UNANTICIPATED ADVERSE DEVICE EFFECT (UADE)

An Unanticipated Adverse Device Effect (UADE) is defined as any serious adverse effect on health or safety or any life-threatening problem or death caused by, or associated with, a device, if that effect, problem, or death was not previously identified in nature, severity, or degree of incidence in the investigational plan or application (including a supplementary plan or application), or any other unanticipated serious problem associated with a device that relates to the rights, safety, or welfare of subjects.

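### Two of the six grounds for leaving the per-protocol set rest on a case-by-case judgement at a blind review meeting with investigators, who are not blinded to arm, and both conflict with the protocol's deviation grades

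*SAP*

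**What the plan says.** SAP 6.4 defines the per-protocol set (PPS) as the full analysis set (FAS) minus subjects with a serious violation, and gives six grounds. Four apply by definition: loss to follow-up, cross enrollment, out-of-specification use, and use of a third-party product. The other two, violation of the eligibility criteria (item 2) and a week-24 visit outside days 140 to 196 (item 5), count only if statisticians, sponsor and investigators "will jointly determine through a blind review meeting whether the protocol violation will seriously affect the results of primary efficacy endpoints". No criteria for that judgement are given. The section does not say which investigators attend, what is masked, or whether the meeting comes before database lock.

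Protocol 7.5 states that "it will not be possible to blind surgeon investigators or study staff" and that medical records "documenting the implant procedure through hospital discharge and all follow-ups will not be blinded". Protocol 7.4 adds: "The Investigator will be required to document clinical assessment in the medical and research source documents". Clinical signs are component 1 of the primary endpoint (Protocol 5.1, SAP 7.3).

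On deviation grades, Protocol Appendix A makes any deviation from the inclusion or exclusion criteria major, and gives "follow-ups performed outside specified time windows" as an example of a minor deviation. Protocol 10.8 removes subjects with major deviations from the per-protocol population and names eligibility failure among them. It adds: "This PP population will be the analysis set for conducting the primary and secondary effectiveness endpoint analyses".

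**The concern.** There are two problems.

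The first is discretion. Membership of the protocol's primary analysis set is settled, for two grounds, by a judgement about effect on the primary endpoint, and the people judging include investigators who are not blinded to arm. Calling the meeting blind does not remove what a treating investigator already knows about their own patient. The four mechanical grounds show that fixed rules are workable in this trial.

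The second is inconsistency. The meeting can retain subjects whom the protocol excludes (eligibility violations) and exclude subjects whom the protocol retains (out-of-window visits).

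With union near 95%, the confidence limit depends on a handful of failures, so a few discretionary removals could bear on the non-inferiority conclusion.

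**Working it through.** **Design figures.** Inputs from Protocol 10.9 and SAP 6.2: union 95% in both arms, margin 10%, one-sided alpha 2.5%, power 80%, attrition 20%.

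- n per arm = 2 × 0.95 × 0.05 × (1.960 + 0.842)² / 0.10² = 74.56, so 75, as stated.
- 75 / 0.80 = 93.75, so 94 per arm, as stated.
- Window: 168 ± 28 days = 140 to 196, which matches ±4 weeks.
- Expected failures per arm: 75 × 0.05 = 3.75, about 4.

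**Passages side by side.**

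| Ground | Protocol 10.8 and Appendix A | SAP 6.3 and 6.4 |
|---|---|---|
| Eligibility violation | Major; excluded | Excluded only if the meeting judges it serious |
| Out-of-window visit | Minor; not an exclusion | Listed as serious; excluded if the meeting agrees |

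**Sensitivity of the limit to removals.** The counts are assumed for illustration. With d = p(TFNA) − p(PFNA-II), non-inferiority needs a lower limit above −10%.

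- Wald: L = d − 1.96 × √[p₁(1−p₁)/n₁ + p₀(1−p₀)/n₀]. This stands in for the SAP's site-adjusted CMH analysis, which needs site-level data.
- Newcombe-Wilson: L = d − √[(p₁−l₁)² + (u₀−p₀)²], where l₁ and u₀ are continuity-corrected Wilson limits. This is the SAP's sensitivity method (SAP 7.3).

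Example: 69/75 against 71/75 gives d = −2.7% and a Wald limit of −10.6%. Removing one TFNA failure gives 69/74 and a limit of −9.1%.

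| Starting counts (TFNA v PFNA-II) | TFNA failures removed | Wald | Newcombe-Wilson |
|---|---|---|---|
| 69/75 v 71/75 | 0 | −10.6% | −12.6% |
| | 1 | −9.1% | −11.1% |
| | 2 | −7.4% | −9.6% |
| 69/75 v 72/75 | 0 | −11.6% | −13.7% |
| | 1 | −9.99% | −12.2% |
| | 2 | −8.3% | −10.7% |
| | 3 | −6.6% | −9.0% |

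Under Wald, one removal reverses either example, the second by only 0.01 points. Under Newcombe-Wilson it takes two removals and three.

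**Worst-case error at the margin.** True rates 85% (TFNA) and 95% (PFNA-II), 75 per arm. All binomial outcomes are enumerated and summed where L > −10%, with k TFNA failures removed in every trial.

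| k | Newcombe-Wilson | Wald |
|---|---|---|
| 0 | 1.5% | 3.7% |
| 1 | 3.3% | 7.1% |
| 2 | 5.6% | 10.6% |

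The Wald row for k = 0 already exceeds 2.5%. That excess belongs to the method, not to the meeting. The effect of removals is the change down each column.

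**The case against.** A data review meeting before analysis is routine, and blind may describe the listings shown there rather than masking at the sites. Whether a violation matters for union can be judged from its type, without knowing whether that patient healed. Protocol 10.8 itself provides for judgement: its list of major deviations is open-ended, includes non-compliance with protocol-specific procedures, and is settled by a review of subject data. Appendix A is not exhaustive either, since Protocol 7.1.4 calls crossover a major violation and Appendix A does not list it. Protocol 10.4 defines the visit windows for analysis purposes. The SAP also analyses the FAS (6.3) and lists every serious violation with its reason and set membership (6.4).

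Much of this stands as a limit on the point. A reader might infer that all PPS exclusions are discretionary, but four of the six grounds are not. A reader might infer that the investigators at the meeting know every outcome. Knowledge of arm is stated; knowledge of outcome is an inference, secure only for an investigator's own patients and for the clinical signs, because the independent reviewer reads the films (Protocol 10.10.5). The documents therefore show that the masking is unspecified and cannot extend to treating investigators. They do not show that the meeting will see unmasked data.

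The open-ended list in 10.8 does not override Appendix A's specific naming of out-of-window visits as minor, and nothing in the protocol makes an eligibility failure conditional. The FAS analysis reduces the risk but does not remove it: SAP 6.3 bases the primary analysis on FAS, PPS and, if applicable, ATS without saying which decides, while the protocol makes the per-protocol set primary.

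**Conclusion.** The point holds for the eligibility and out-of-window grounds. The SAP states a discretionary rule, involves people the protocol describes as unblinded to arm, and contradicts the protocol's grading in both directions. This is more than missing detail, because the stated rule itself needs replacing.

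The error rates in the worst-case table are ceilings. They assume that a TFNA failure is removed in every trial, whereas a real removal needs a failure who also has an eligibility or window violation, and agreement at the meeting. They also rest on 75 evaluable per arm, true rates at the margin, and limits that are neither the SAP's site-adjusted CMH analysis nor the exact bound in Protocol 10.10.5. A reader might take the Wald example to mean that a single exclusion would overturn the trial; the SAP's own Newcombe-Wilson method does not support that. A modest correction is warranted, and it is cheap.

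**What to change.** Amend SAP 6.3, 6.4 and the notes to the population tables before database lock:

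- **Eligibility:** every violation of an inclusion or exclusion criterion excludes the subject from the PPS, as Protocol 10.8 and Appendix A already require.
- **Window:** subjects seen outside days 140 to 196 stay in the PPS as a minor deviation, with a sensitivity analysis restricted to that window. If the sponsor prefers to exclude them, exclude all of them by rule and amend Appendix A.
- **Any remaining classification:** make it from listings without arm, implant data or week-24 outcome, by people who did not treat the subjects, and sign it before outcome data are opened.

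The cost is wording and less flexibility at the review meeting. Automatic eligibility exclusions may also shrink the set slightly: at 72 instead of 75 evaluable per arm, power is 78.6% instead of 80.2%. The alternative window rule would also need a protocol amendment.

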8.5. Reporting an Adverse Event

Adverse events are reported from the start time of the index procedure until the subject's study participation has ended (i.e. revision, completion of study or withdrawal of consent). All AEs must be followed until the AE has resolved, stabilized, or the study has been completed.

The Investigator will record the nature, severity, treatment and outcome of the AE, and will

determine the relationship to the investigational products, medications or any protocol mandated procedures involved in the clinical study.

The following categories of adverse event severity are to be used:

Mild:	Awareness of sign or symptom that does not interfere with the subject's
	usual activity or is transient, resolved without treatment and with no
	sequelae,
Moderate:	Interferes, but does not hinder, the subject's usual activity and may
	require treatment,
Severe	Symptom(s) causing severe discomfort and significant impact on the
	subject's usual activity and requires treatment or intervention.

The causal relationship should be rated as follows:

Unrelated:	The event is definitely not associated with product application
Unlikely:	The temporal sequence between product application and the event is such that the relationship is unlikely,
Possible:	The temporal sequence between product application and the event is such that the relationship is not unlikely or the subject's condition or concomitant therapy could have caused the AE,
Probable:	The temporal sequence is relevant or the event abates upon product application completion or the event cannot be reasonably explained by the patient's condition,
Related:	The temporal sequence is relevant and the event abates upon product application completion or reappearance of the event on repeat product application (re-challenge).

Adverse events will be reported by the investigator to the Sponsor via the CRF.

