9.2. Subject Early Discontinuation

Every subject should be encouraged to remain in the study until they have completed the protocol-required 24-week follow-up period. If the subject discontinues prematurely from the study, the reason for discontinuation must be documented in the source documents and site files, and submitted via CRF.

Subjects who have discontinued prematurely will be included in the analysis of results; however new subjects may not be enrolled to replace these subjects.

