10.10.5 Analysis of the primary endpoint

In accordance with ICH guidance E9(²)the primary endpoint analysis will be based on the Per-Protocol set of patients for a comparison of the fracture union rates at Week 24 between TFNA and PFNA-II. Only patients in this analysis set with a known outcome for the primary endpoint will be analyzed.

The null hypothesis (TFNA is inferior to PFNA-II) will be rejected, and TFNA will be considered non-inferior to PFNA-II if the exact 97.5% upper one-sided confidence bound for the difference in fracture union rates between PFNA-II and TFNA at 24 weeks is less than non-inferiority margin, 10.0%.

Two sub-components of the primary endpoint at 24 weeks (radiographic outcome, and no deformation or breakage) will be compared between the two treatment groups.

Radiographic outcome, i.e. front/lateral X-ray films, will be assessed by the independent radiographic reviewer to determine if there are vague or fracture gap or continuous callus passing across the fracture line. The radiographic outcome will be summarized and compared at each follow up visit between the two treatment groups using Fishers exact test.

Similarly, the independent radiographic reviewer will also determine whether deformation or breakage of the implant has occurred. This outcome will be summarized between the two treatment groups at each follow up visit, as well.

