7.3 Primary endpoint

The primary endpoint is the fracture union rate 24 weeks after surgery.

Fracture union success is a composite endpoint; in order for an individual subject's surgery implanted with TFNA or PFNA-II to be considered successful he/she must satisfy all of the following criteria:

- 1. No focal tenderness or lengthwise percussion pain, or abnormal movement
- 2. The frontal/lateral X-ray examination shows the vague or no fracture gap, or the continuous callus passing across the fracture line
- 3. No deformation or breakage is found in the investigational product

Calculation principle: Based on the postoperative 24-week follow-up of the fracture status and the X-ray examination results of the fracture site, the calculation principle is as follows:

- 1. It is determined as 'Yes' when the focal tenderness, lengthwise percussion pain and abnormal activity at the postoperative 24-week follow-up of the fracture are filled as 'NA', 'NA' and 'No', respectively;
- 2. It is determined as 'Yes' when the X-ray examination at the fracture site 24 weeks after surgery shows that the fracture line is 'vague' or 'disappeared'; or that the frontal/lateral X-ray examination shows the continuous callus passing across the fracture line is filled as 'Yes';
- ③. It is determined as 'Yes' when the X-ray examination at the fracture site 24 weeks after surgery shows that the implant is filled as 'good';

If (1), (2) and (3) are determined as 'Yes', then the successful fracture union 24 weeks after surgery is determined as 'Yes'; if one of them is missing, it is determined as missing, that is, 'loss to follow-up during the trial'; others are determined as 'No';

For the primary endpoint, the analysis bases on the actual data (except missing data). LOCF (Last Observation Carry Forward) was used as sensitivity analysis for the missing of primary efficacy endpoints. The below 2 analysis tests will be used for the above analysis, and estimates of the differences in efficacy between the groups and bilateral two-sided 95% confidence interval will be given:

(1) CMH chi-square test with adjusted central effects;

Calculation method for non – inferiority P value:

Se=(Rate difference 95% upper limit of confidence interval - Rate difference 95% low limit of confidence interval)/2/ probit (1-0.05/2);

Z=(Investigational group-control group of difference in fracture union rates- non-inferiority margin)/Se;

P value=1-probnorm(Z);

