2. The likelihood ratio Chi-square test or Fisher's exact probability test is used to analyze the intergroup comparison of qualitative indicators;

			-	
Indicator	Study group	Control group	Statistics	P value
Successful fracture union 24 weeks at	ter surgery ^{#1}			
Number of subjects (N miss)	XXX (XXX)	XXX (XXX)	X.XXXX	X.XXXX
Yes	XXX (XX.X%)	XXX (XX.X%)		
No	XXX (XX.X%)	XXX (XX.X%)		
Difference in success rate (study group - c	ontrol group) and 95% CI	XX.X% [XX.X	%; XX.X%]	
P value in non-inferiori	e 1/	X.XXXX		
Difference in success rate (study group - c	ontrol group) and 95% CI	XX.X% [XX.X	%; XX.X%]	
P value in non-inferiori	ty test #4	X.XXXX		
Successful fracture union 24 weeks at	ter surgery ^{#2}			
Number of subjects (N miss)	XXX (XXX)	XXX (XXX)		
Yes	XXX (XX.X%)	XXX		
		(XX.X%)		
No	XXX (XX.X%)	XXX		
		(XX.X%)		
Difference in success rate (study group - c	ontrol group) and 95% CI	XX.X% [XX.X	%; XX.X%]	
P value in non-inferiori	ty test #3	X.XXXX		
Difference in success rate (study group - c	• •	XX.X% [XX.X	%; XX.X%]	
P value in non-inferiori	ty test #4	X.XXXX		

Table 30 (FAS) Primary endpoint - Statistical analysis results of subjects'fracture union rate 24 weeks after surgery

Notes: 1. #3 is analyzed by CMH chi-square test with adjusted sites, estimate the difference in success rate and non-inferiority test the P value;

#4 is analyzed by Continuous correction Newcombe-Wilson for non-adjusted central, estimate the difference in success rate and non-inferiority test the P value;

2. #1: The primary efficacy indicators of the subjects lost to follow-up during the trial were not processed;

#2: The primary efficacy indicators of the subjects lost to follow-up during the trial were carried forward by LOCF;

3. If the lower limit of 95% CI of the difference in the rates of the study group and the control group is greater than the non-inferiority margin of -10%, then the investigational product is considered non-inferior to the control product, i.e., the non-inferiority conclusion is established in this trial.

Indicator	Study group	Control group	Statistics	P value
Site 01 Beijing Jishuitan Hospital - Su	accessful fracture unio	on 24 weeks after su	rgery	
Number of subjects (N miss)	XXX (XXX)	XXX (XXX)	X.XXXX	X.XXXX
Yes	XXX (XX.X%)	XXX (XX.X%)		
No	XXX (XX.X%)	XXX (XX.X%)		
Site 02 Peking University Third Hosp	ital - Successful fract	ure union 24 weeks	after surgery	
Number of subjects (N miss)	XXX (XXX)	XXX (XXX)	X.XXXX	X.XXXX

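### SAP 7.3 applies its missing rule before any failure rule and never scores revision, so a subject with a known device failure may leave the primary non-inferiority test instead of counting against the device

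*SAP*

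**What the plan says.** The composite in SAP 7.3 has three parts, all read from the week-24 visit: clinical signs, fracture line or callus on X-ray, and implant state. If all three are met the subject is a success. The next rule is "if one of them is missing, it is determined as missing, that is", in the SAP's own label, loss to follow-up during the trial. Only subjects left after that step can become 'No'.

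SAP 6.4(3) uses the same label: "Loss to follow-up during the trial: Subjects are unable to obtain the fracture union rate 24 weeks after the primary endpoint surgery". SAP 6.4(8) counts these subjects among the serious violators and sets "PPS = FAS - Number of subjects who seriously violate the study protocol". They remain FAS members, but SAP 7.3 states "For the primary endpoint, the analysis bases on the actual data (except missing data", and the Table 30 notes say of the main row: "The primary efficacy indicators of the subjects lost to follow-up during the trial were not processed". Protocol 10.10.5 is similar for its per-protocol analysis: "Only patients in this analysis set with a known outcome for the primary endpoint will be analyzed".

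Protocol 8.5, which sets the adverse event reporting period, describes it as lasting until "study participation has ended (i.e. revision, completion of study or withdrawal of consent". Neither protocol 5.1 nor SAP 7.3 mentions revision in the definition of success. SAP 7.4(2) scores revision up to day 196 as a separate secondary endpoint.

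**The concern.** There are three gaps.

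- **Observed failures can be discarded.** A ruptured nail on the week-24 X-ray with a blank tenderness entry is missing, not 'No'.
- **Revision before week 24 has no score.** If the subject has no week-24 assessment, the failure leaves the PPS and the main FAS row.
- **A revised subject who returns is judged on the implant then in place.** A replacement recorded as 'good' can support a success.

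Removal of the implant is the clearest failure in a nail trial. In a non-inferiority test, leaving out failures that occur more often on the test device biases the comparison towards the margin being met.

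**Working it through.** **Plan's own figure.** Inputs from SAP 6.2 and 6.6: success 95% in both arms, margin 0.10, one-sided alpha 0.025, power 80%. n = 2 × 0.95 × 0.05 × (1.96 + 0.8416)² / 0.10² = 74.56, so 75 per arm. With 20% attrition, 75 / 0.8 = 93.75, so 94 per arm. Both stated figures reproduce.

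**Illustration.** The documents give no revision rate for this trial, so the counts are assumed: 94 per arm, 4 other failures in each arm, 4 TFNA and 0 PFNA-II revisions, all revised subjects without a week-24 result. The unstratified Wald limit stands in for the site-adjusted CMH interval: lower limit = d − 1.96 × √(p₁q₁/n₁ + p₂q₂/n₂).

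| Handling | TFNA | PFNA-II | d | SE | Lower limit | Against −10% |
|---|---|---|---|---|---|---|
| Revised dropped | 86/90 | 90/94 | −0.2% | 3.01% | −6.1% | passes |
| Revised counted as failures | 86/94 | 90/94 | −4.3% | 3.55% | −11.2% | fails |

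The SAP's continuity-corrected Newcombe-Wilson interval gives −7.9% and −12.8%, with the same two conclusions. Three revisions do not reverse the Wald result (87/94 against 90/94, lower limit −9.9%). Two are enough with Newcombe-Wilson (−10.2%).

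**Chance of declaring non-inferiority.** Simulation of 400,000 trials: 94 per arm, 95% success among unrevised subjects, no other attrition, assumed revision 4.3% on PFNA-II and 8.6% on TFNA, no revised subject with a week-24 result. Non-inferiority is declared in 85% of trials if revised subjects are dropped and 26% if they are counted. Here true success with revision as failure is 0.95 × 0.957 = 90.9% against 0.95 × 0.914 = 86.8%, a deficit of 4.1 points. That lies inside the margin, so these figures show how much the verdict depends on the rule. They are not an error rate.

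**Type I error.** Put TFNA exactly on the margin (true success 85% against 95%), with PFNA-II revision 2% and 94 per arm:

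| Assumed TFNA revision | Dropped | Counted |
|---|---|---|
| 2% | 3.5% | 3.3% |
| 4% | 8.9% | 3.3% |
| 6% | 20.6% | 3.3% |
| 8% | 40.9% | 3.3% |

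At equal revision there is almost no inflation. The harm comes from an imbalance between arms.

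**Effect of the fix on power.** It depends on what the planning 95% means.

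- If it already counts revised subjects as failures, nothing changes.
- If union is near 100% among unrevised subjects, as in the 389 PFNA-II subjects of protocol 1.3.3, 4.3% revision gives 95.7%. Then n = 2 × 0.957 × 0.043 × 7.849 / 0.01 = 64.6, so 65 per arm, below the planned 75.
- If 95% applies to unrevised subjects and 4.3% are revised in both arms, success is 90.9% and 130 evaluable per arm are needed. Simulated power at 94 per arm is 67% with no other attrition. With 20% attrition it is 55% if only unrevised subjects drop out, and about 58 to 59% if attrition falls on everyone.

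**The case against.** A reader might infer that every revised subject is excluded from the primary test. The documents do not say that. The link rests on a parenthesis in protocol 8.5 about how long adverse events are reported. Protocol 9.1 does not list revision among its (non-exhaustive) reasons for discontinuation, and 9.2 encourages every subject to stay to week 24. SAP 7.4(2) treats revision and failed week-24 follow-up as different things. Protocol 9.2 also says "Subjects who have discontinued prematurely will be included in the analysis of results", which the main rows do not honour for a subject without a week-24 result. So a revised subject may drop out of the test, and how many would is unknown.

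A reader might also infer that such failures would be hidden. They would not. The FAS LOCF row in Table 30 has its own interval and non-inferiority P value and scores nonunion unless union was definitive. The revision and reoperation rates are reported as well. But SAP 6.5 and 7.3 both label LOCF a sensitivity analysis, and Tables 32 and 33 (PPS and ATS) have no LOCF row.

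Nor is a returning revised subject automatically a success: any recorded implant state other than 'good' gives 'No' once all components are present. The SAP does not say how a removed or replaced implant is entered. A blank examination entry beside a week-24 X-ray should be rare, because missing data are queried (protocol 10.10.3).

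Finally, the rates are assumptions. Protocol Table 4 shows PFNA-II cut-out of 4.3% and reoperation of 6.5%, but these come from one trial with 47 PFNA-II subjects and are not component-removal rates. They make the assumed range plausible and no more.

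**Conclusion.** The point stands as a gap in the scoring rule. As written, missing takes precedence over observed failure, and nothing makes revision a failure. Both features favour whichever device is revised more often. The size depends on how many revised subjects lack a week-24 result and on the imbalance between arms. If all lack one, four TFNA revisions against none are enough to turn a failing Wald result into a passing one. If revised subjects attend and their implant is not recorded as 'good', the effect shrinks or disappears. The documents do not support saying that known device failures will drop out, only that they may, and that the decisive test has no rule to prevent it. This should be settled before the data are unblinded to the analysts.

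**What to change.** In SAP 7.3, ahead of the missing rule, add: 'A subject revised before the week-24 assessment (or by day 196 if there is none), or who fails any observed component at week 24, is determined as No, whatever else is missing.' Keep such subjects in the FAS, and in the PPS unless another serious violation in SAP 6.4 applies. Amend 6.4(3), and the notes that repeat its definition under Tables 1 and 4 to 13, to match. State whether removing a locking screw for planned dynamization counts as revision, with a sensitivity analysis the other way.

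Protocol 5.1 (success criteria), 10.8 (completion of 24 weeks for the per-protocol set) and 10.10.5 (known outcomes only) need aligning, which probably means an amendment under protocol 12.4.

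The cost is a short SAP edit plus that alignment. SAP 7.4(2) already takes revision and its date from the adverse event data in the CRF, so no new visits or fields are needed. The possible price is power: about 67% with no other attrition, and 55 to 59% with 20%, if the planning 95% excludes revised subjects and 4.3% are revised in both arms. The sponsor should state what the 95% means.
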